#### **7. INTERVENTION**

*Treatment:* PECS is a well-established manualised system for teaching children to communicate using pictures . It involves 6 developmental stages, each focusing on specific communication skills. PECS uses behavioural strategies to teach children to exchange a picture-card or object for an immediate high value reward (e.g. favourite food). Initially, teaching is primarily through the use of physical prompts, which are subsequently systematically faded to ensure independence.

- Stage 1: focuses on teaching the child to exchange an image to receive a highly desirable item (often food). Prompts are given by a second adult and prompting is then gradually reduced.
- Stage 2: develops a child's persistence by creating small barriers to communication such as increasing the distance between the child and the desired object/activity.
- Stage 3: more images of desired items are introduced and the child begins to discriminate between them to make requests.
- Stage 4: combines images in a "picture strip" to indicate messages such as 'I want....', thereby helping the child to use more complex constructions.
- Stages 5 and 6: build on these skills to help a child learn to answer questions (e.g. what do you want?) and to make comments (e.g. what can you see?)

In this study we anticipate that most children will complete Stages 1-3.

Delivery of therapy: Parents will be provided with detailed information about the study and introduced to the PECS treatment techniques and phases. The therapist will then provide 6 weekly sessions at home with the parent and child, followed by a further 6 home-based sessions on a fortnightly basis, giving a total of 12 sessions over 18 weeks. Timings for homebased sessions and assessments will be arranged to fit in with parents' other commitments. All children will start the PECS treatment at Stage 1 even if they are beyond that phase in school. This is to ensure that parents, who are unlikely to have participated in school based PECS schemes, are confident in using the system. Start and end point Stages for all children will be recorded. A brief summary report will be provided to families at the end of the intervention. This report will detail the number of sessions attended, the progress the child has made and the PECS Phase achieved with a brief description of skills at this PECS Phase.

## 8. STUDY OUTCOMES

As this study is designed as a feasibility study primary outcome data will focus on the following variables:

- a) Successful recruitment strategy i.e. recruitment of 64 eligible participants
- b) Data collection on questionnaire and direct assessments for all participants at each assessment time point
- c) Utility of the App and body-worn cameras and quality of data obtained from this equipment.
- d) Retention of families in both groups,
- e) Number of home-based sessions delivered by the therapist
- f) Evaluation of the PECS stages established for treatment families (parent treatment fidelity)
- g) Child and Adolescent Service Use Schedule (CA-SUS) to ascertain local provision
- h) Parent, teacher, research assistant and therapist feedback on feasibility and acceptability (Social Validity Questionnaire, focus groups).

The secondary outcome data will focus on the following:

a) PECS usage - (telephone App and video). The RA will extract frequency counts from the App and score episodes of requesting from films (remaining blind to group allocation).

Experience of coding behaviour from video suggests that it should be possible to scroll through the video at a medium-fast forward pace to identify episodes of requesting behaviour and then to score them according to 2 codes: 1) use of PECS, 2) other forms of request (e.g. speech, vocalisations or gestures etc.)

b) Communication Development Inventory (CDI) to explore whether there has been any overall change in children's communication skills.

Additional outcome data:

a) A short anonymous questionnaire to explore children's access to PECS intervention from professionals working with children with autism. The questionnaire will be circulated through professional Clinical Excellent Networks (CENs) via Survey Monkey. It is designed to take under 10 minutes to complete, consisting mainly of multiple choice questions.

b) A short anonymous questionnaire to ascertain if individuals transferring to adult services do so with some skills using PECS and also to establish if PECS is included in treatment for adults. The questionnaire will be sent through professional Clinical Excellence Networks (CENs) to professionals working in adult therapy services via Survey Monkey. It takes under 10 minutes to complete and is mainly comprised of multiple choice questions.

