#### 6.2. PECS usage

PECS is specifically designed to increase spontaneous communication and our focus is on the feasibility of assessing truly spontaneous requests (i.e. unprompted by a task or context) in the home. Changes in such behaviours cannot easily be captured in a short assessment session and recordings made by an unknown observer in the home are likely to interfere with natural communication. Thus, we aim to acquire parent rated and independent verification of the frequency and types of spontaneous requests made by the child at home using two novel approaches to data collection:

a) App for use on smartphones (i.e. Tally Tracker App). Parents will be asked to use the App supplied by the research team, to make frequency counts of: a) requests made using PECS; b) requests made by other means (e.g. speech, vocalisations or gestures etc.);. Any other forms of communication will be recorded in an 'other' category as qualitative data.

The researcher will provide the app and assist all participants in downloading it on their mobile phones. Two app step-by-step guides (i.e. for iPhone and android) will also be given to parents. The app is easy to use and does not involve complex features. Use of the App at these pre-specified times will be prompted by a text from the research assistant [name].

- b) Video recording using a very small body camera (approximately 4cm x 2cm), worn by the child (as used by cyclists; see appendices). This equipment will provide corroborative information about the frequency and type of spontaneous communication used by the child at home. Personal communication from two parents who were asked to use the cameras and report back to the study team (one typically developing child and one with autism) have confirmed acceptability after a short period of acclimatisation details). Families will be given a defunct camera prior to the recording sessions in order to allow the child to become comfortable with the device. Cameras will be supplied via the research team. A step-by-step guide on how to use the camera will be provided to parents. All data will be removed from the camera and stored on an encrypted hard drive by a designated member of the study team.

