#### 9. STATISTICAL ANALYSIS

The similarity of data derived from the App and video will be compared to establish the respective value of these sources of data. Parental counts (via telephone App) and video recordings of number of spontaneous requests used by the child will be analysed using intention-to-treat approach in a mixed ANOVA model, accounting for clustering within school and covarying for baseline score on the same measure. This will inform the sample size for a possible full randomised control trial. A preliminary power calculation (2-tailed p=.05 and assuming 10% drop-out or failure of equipment) indicates that the study has 47% power, for an effect size of 0.5 and 62% power for an effect size of 0.6 on the secondary measure of rate of spontaneous requests using PECS. Change in vocabulary use (assessed by the CDI) will also be compared across groups. In addition we will explore the impact on outcome of child characteristics e.g. age, developmental level and parental fidelity to treatment as rated by the therapist (see measures).

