#### Data handling and confidentiality

Data will be processed in accordance with the General Data Protection Regulation 2016 (GDPR). All research data is stored separate from personal data, using a unique code. Any information shared with third parties will be anonymised. No video or audio data will be used without consent. All information which is collected during the research will be kept strictly confidential as follows:

a) Paper assessments such as questionnaires, contact details, consent forms and correspondence with families and schools. These will stored in such a way as to keep study identity numbers and personal details (i.e. contact details) separately. These papers will be collected from parents or school staff in person unless there is agreement for them to be posted or sent by encrypted email to the study team. We will store all therapy related papers in a locked cabinet in a secure location at the Evelina Children's Hospital (Becket House) and research documents at the Institute of Psychiatry, Psychology & Neuroscience (IOPPN) (Henry Wellcome Building).

- b) The tally counts from parents' mobile phones will be easily downloaded by parents and send to a nominated member of our research staff via encrypted email. These data will be stored on an encrypted external hard drive by a designated member of the research team.
- c) Video recordings from the camera will be downloaded and stored in an external encrypted hard drive by a member of the research team. Only authorised members of the research team will have access to this data.
- d) Computer files will be stored on devices that are encrypted (protected) and kept separately in password protected storage.
- e) No identifying information will appear on any other reports or presentations produced by the study team. For further educational use of these video clips, for example for research dissemination, participants will be contacted and consented in all cases.

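### The film scorer is masked to allocation but not to the parent's App count, so App–video agreement may be inflated

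*Protocol*

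**What the plan says.** The App counts come from parents. Section 6.2 states: "Parents will be asked to use the App supplied by the research team, to make frequency counts of" requests made with PECS and requests made by other means. The child also wears a camera, about which the same section says: "This equipment will provide corroborative information about the frequency and type of spontaneous communication used by the child at home". The purpose of having both is given there too: "we aim to acquire parent rated and independent verification of the frequency and types of spontaneous requests made by the child at home".

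Section 8, secondary outcome a), says who handles the two sources: "The RA will extract frequency counts from the App and score episodes of requesting from films (remaining blind to group allocation". It describes the film work as a search, in which the scorer is expected to "scroll through the video at a medium-fast forward pace to identify episodes of requesting behaviour" and then give each episode one of two codes (PECS, or another form of request such as speech, vocalisation or gesture).

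Section 9 sets out the use: "The similarity of data derived from the App and video will be compared to establish the respective value of these sources of data". The utility of the App and cameras, and the quality of the data they yield, is also primary feasibility outcome c) in Section 8.

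Section 12 (Data handling and confidentiality, item b) says that the tallies "will be easily downloaded by parents and send to a nominated member of our research staff via encrypted email". It does not say whether that person is the RA.

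**The concern.** A comparison of two measurement methods is informative only if each reading is made without knowledge of the other. Here the person who finds and codes requests on film is also the person who reads off the parent's count for the same child, and the only masking stated is to treatment group. Masking to allocation does not deal with this. A scorer who has no idea of the child's group, but knows that the parent logged 20 requests and has found 12 on film, has a reason to look again. (The 20 and 12 are an invented example.)

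There is room for judgement. The films are searched at speed, the children have fewer than ten words in regular use, and whether a sound or gesture was a spontaneous request is often debatable.

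Two things are at stake. The first is the App–video comparison, which informs a primary feasibility outcome. The second is the film count as an outcome in its own right. Parents deliver the treatment and know their allocation, so part of any tendency to over-count in one group could pass into the film measure, which Section 9 analyses to inform the sample size of a full trial.

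**Working it through.** **Passages side by side**

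- Who makes the App count: the parent (Section 6.2; Section 9 also calls these parental counts).
- Who extracts it: the RA (Section 8).
- Who scores the film: the RA (Section 8).
- What the RA is masked to: allocation only (Sections 5.3, 5.4 and 8).
- Order of extraction and scoring: not stated.
- Second coder: none stated.
- Who receives the tallies: a staff member whose role is not named (Section 12 b). Section 6.2 adds that the RA's text message prompts each App session, which puts the RA close to the App data but does not show that the RA sees the counts before scoring.

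**The plan's own figures**

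The protocol gives no expected correlation, agreement statistic or rater-bias figure, so there is nothing on this point to reproduce. Its only design figures are the powers in Section 9. With 32 × 0.9 = 28.8 per group, two-sided 5% and a normal approximation, power is 47.5% at an effect size of 0.5 and 62.4% at 0.6, which matches the stated 47% and 62%. This point does not depend on those figures.

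**Illustration of size (assumptions, not document figures)**

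Let A be the App count and F the film score that would be given without sight of A. Assume that they have equal variance and true correlation r. Suppose the recorded film score is pulled a fraction w of the way towards A:

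F′ = (1 − w)F + wA

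Then

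corr(F′, A) = [(1 − w)r + w] / √[(1 − w)² + w² + 2w(1 − w)r]

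For r = 0.60 and w = 0.3: the numerator is 0.7 × 0.60 + 0.3 = 0.72, the denominator is √(0.49 + 0.09 + 0.42 × 0.60) = √0.832 = 0.912, and the ratio is 0.789.

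For r = 0.40 and w = 0.3: the numerator is 0.58, the denominator is √(0.58 + 0.168) = √0.748 = 0.865, and the ratio is 0.671.

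| Pull w | observed if r = 0.40 | observed if r = 0.60 |
|---|---|---|
| 0 | 0.40 | 0.60 |
| 0.1 | 0.49 | 0.66 |
| 0.2 | 0.58 | 0.73 |
| 0.3 | 0.67 | 0.79 |

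The mean film–App difference is multiplied by (1 − w), so it shrinks by 0 to 30% over the same range. A between-group difference δ in parental over-counting would enter the film outcome as wδ. With δ = 0.3 SD, again assumed, that is 0 to 0.09 SD.

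The direction is fixed by the algebra: under this model, any positive w raises the correlation and narrows the mean difference. The size of w cannot be had from the protocol.

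**The case against.** A reader might infer that the film is no independent check at all, or that agreement is bound to be inflated. The protocol supports neither. The parent makes the App count and the RA only transcribes it, so the film is still rated by someone other than the parent. Section 8 gives no order for the two tasks. Scoring first and extracting afterwards would comply with the text and produce no inflation.

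Other limits also stand:

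- A PECS exchange is a visible, discrete act and leaves less room for drift than a vocalisation or gesture. The power statement concerns requests using PECS.
- Section 6.2 sets periods of 2–3 hours for the App but none for the camera, so a child's App total may not be a direct target for the film score.
- Aim (d) in Section 5.1 concerns the feasibility and acceptability of cameras, not whether they add to the App, so it should not be used to enlarge the point.
- Section 9 sets no agreement threshold on which a decision would turn.

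It can also be said that scoring order belongs in a coding manual or an SAP. That answers a complaint about a missing agreement statistic, which is not made here. It does not fully answer this point. Section 8 itself fixes who scores and what the scorer is masked to, and as written it leaves the scorer free to know the count that the film is meant to check.

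**Conclusion.** The point holds as a gap in protection, not as a demonstrated bias. Section 8 can be followed to the letter while the film score is anchored on the App count, and the verification in Section 6.2 and the comparison in Section 9 both rely on that not happening. Apparent agreement may therefore be inflated.

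The size is unknown. For an assumed pull of 0 to 30% with equal variances, a true correlation of 0.60 would be observed as 0.60 to 0.79, and 0.40 as 0.40 to 0.67. The lower end of each range is no inflation, and the documents do not exclude it. It would go too far to say that the App would look accurate and the camera redundant whatever the truth. The change is worth making because it is cheap and protects a comparison that bears on a primary feasibility outcome.

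**What to change.** Add to Section 8, secondary outcome a): each child's films are scored, and the scores locked, before the scorer sees any of that child's App counts. This should cover all time points, since a baseline tally could colour the scoring of a later film.

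Clarify in Section 12 b) who receives the tallies. If it is not the RA, that person can hold them until the film scores are locked. If it is the RA, the tallies should stay unopened until then.

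If films have already been scored, report the order in which the two tasks were done. Section 12 c) says the recordings are kept on an encrypted drive, so while they are retained a sample could be re-scored by someone who has not seen the App counts.

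The prospective change costs a sentence in each of two sections and needs no extra staff. Re-scoring a sample would take some of a second person's time. The drawback is delay: the RA cannot extract or check a child's App tallies until film scoring for that child is complete, so a missing or faulty tally may come to light later unless someone else checks it on receipt. Sample size and power are unaffected.

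### The film codes and App counts record only the mode of a request, so prompted picture exchanges could be counted as spontaneous; fast-forward viewing separately risks missing audible requests

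*Protocol*

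**What the plan says.** Protocol section 6.2 states the target of measurement as "truly spontaneous requests (i.e. unprompted by a task or context) in the home". Parents use the App to make "frequency counts of: a) requests made using PECS; b) requests made by other means", with any other communication noted as qualitative data. The App and the child-worn camera together are to give parent ratings and "independent verification of the frequency and types of spontaneous requests made by the child at home".

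Section 8, secondary outcome a), has the blinded research assistant take counts from the App and score the films. Prior experience is said to suggest that "it should be possible to scroll through the video at a medium-fast forward pace to identify episodes of requesting behaviour", after which the coder is to "score them according to 2 codes: 1) use of PECS, 2) other forms of request (e.g. speech, vocalisations or gestures etc".

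Section 7 describes how the treated arm learns the system: "Initially, teaching is primarily through the use of physical prompts, which are subsequently systematically faded to ensure independence". At Stage 1 a second adult gives the prompts. All treated children start at Stage 1, and most are expected to complete Stages 1 to 3.

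Section 9 compares App with film, then analyses the number of spontaneous requests from each source by intention to treat, adjusting for baseline and for clustering by school. The power statement in the same section refers to a narrower quantity, the rate of spontaneous requesting by PECS.

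**The concern.** The outcome is defined by whether a request was prompted, but the stated scoring records only how it was made. Nothing in the film codes or the App categories keeps a prompted exchange out of a count that is then analysed as spontaneous. Prompting is part of what treated parents are taught, so the error is likely to be commoner in the PECS arm. Blinding the coder does not remove it, because it lies in the rule and not in the coder's judgement. Baseline adjustment does not remove it either, because trained prompting begins after baseline. The distinction is central to the trial's rationale: section 4 criticises school use of PECS because requests there are cued by the situation.

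A second, separate risk lies in how episodes are found. The second film code includes speech and vocalisations, which are easily missed at fast-forward. The protocol does not say whether sound is followed.

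This reaches beyond one secondary outcome. Film is the check on unblinded parent counts, the quality of camera and App data is itself a primary feasibility outcome (section 8, item c), and the counts are to inform the sample size of a full trial. If App and film both admit prompted exchanges, they can agree and both be wrong.

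**Working it through.** **1. The plan's own figure.** The only numbers attached to this outcome are the power figures in section 9. With 32 per arm and 10% loss, n = 32 × 0.9 = 28.8 per arm, and power ≈ Φ(d·√(n/2) − 1.96).

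- d = 0.5: Φ(0.5 × 3.795 − 1.96) = Φ(−0.063) = 47.5%, against 47% stated.
- d = 0.6: Φ(0.6 × 3.795 − 1.96) = Φ(0.317) = 62.4%, against 62% stated.

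The figures reproduce. They do not bear on the measurement question, except that they name the PECS-only rate as the outcome powered.

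**2. Definition against scoring.**

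| Element | Prompted v unprompted | PECS v other mode |
|---|---|---|
| Target (6.2) | Yes: unprompted only | Types of request also of interest |
| App counts (6.2) | Not recorded | Recorded |
| Film codes (8) | Not recorded | Recorded |
| Analysed counts (9) | Described as spontaneous | All modes; PECS only in the power statement |

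The attribute that defines the outcome is absent from both data sources as described.

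**3. Direction of each error.** The protocol gives no rate of prompting or detection, so every value here is assumed, to show direction only. Let T be true unprompted requests per recording, equal in both arms. Let s₁ and s₀ be the shares made by PECS in the PECS and TAU arms, a and b the proportions of PECS and other requests detected, and p the prompted exchanges scored, as a fraction of unprompted ones (the same p in both arms).

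- Recorded PECS count = T·s·a·(1+p)
- Recorded other count = T·(1−s)·b
- Arm difference in total = T(s₁−s₀)[a(1+p) − b]; the true difference is 0
- Arm difference in PECS-only count = T(s₁−s₀)·a(1+p)

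With T = 10, s₁ = 0.5, s₀ = 0.1 and a = 0.95, T(s₁−s₀) = 4, which is the true PECS-only difference.

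| b | p | Total | PECS-only |
|---|---|---|---|
| 0.95 | 0 | 4(0.95−0.95) = 0 | 3.80 |
| 0.80 | 0 | 4(0.95−0.80) = 0.60 | 3.80 |
| 0.60 | 0 | 4(0.95−0.60) = 1.40 | 3.80 |
| 0.95 | 0.2 | 4(1.14−0.95) = 0.76 | 4.56 |
| 0.95 | 0.4 | 4(1.33−0.95) = 1.52 | 5.32 |
| 0.60 | 0.4 | 4(1.33−0.60) = 2.92 | 5.32 |

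With s₁ = 0.3 every entry halves: the non-zero totals shown run from 0.30 to 1.46.

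**4. Reading the table.** Lowering b moves the total but never the PECS-only difference. Its effect on the total vanishes if s₁ = s₀. Raising p moves both. If only the PECS arm has prompted exchanges, the row b = 0.95, p = 0.4 gives 11.40 − 9.50 = 1.90 on the total instead of 1.52.

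**The case against.** The strongest reply is that the two film codes may be meant to classify episodes already judged spontaneous under the section 6.2 definition. Parents also receive step-by-step guides, not shown here, that may tell them what to tally. That reading is possible, but no rule in the protocol says so, and the categories as written would admit a prompted exchange. The gap in the stated scheme stands.

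Several other points on this side also stand:

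- The viewing pace is worded as what should be possible, with finding and scoring as two steps. Nothing says the sound is off. Loss of audible requests is a risk, not a stated feature.
- Prompts are to be faded, and outcome films are taken after treatment and at follow-up. The share of exchanges still prompted by then is unknown and may be small.
- Prompted speech or gesture could enter the second code in either arm. If it did so at rate q, the total difference becomes T(s₁−s₀)[a(1+p) − b(1+q)], which is zero when a = b and p = q. The inflation of the PECS-only count would remain.
- Gestures are visible at speed, and eligible children use fewer than 10 words, so the loss under the second code may be limited.

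A reader might infer that both errors favour the PECS arm on every count. The document does not support that: missed audible requests leave the PECS-only rate unbiased and affect the total only through a difference in mode mix. A reader might also infer that film simply shares the parents' bias. That could be so for prompted exchanges, but not for fast-forward loss: parents count live, and a shortfall on film could show up in the App-film comparison.

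**Conclusion.** The point holds in two parts of unequal strength. The firmer part is that the scoring described does not isolate the outcome defined and analysed. Prompted exchanges could be counted as spontaneous, which would tend to inflate the PECS arm on both the PECS-only and the total count. This rests on some prompting continuing in recording windows and on no unseen instruction excluding it. The weaker part is that fast-forward viewing risks under-detecting speech and vocalisations. This would bias the all-mode total if the arms differ in mode mix and would distort the App-film comparison, but not the PECS-only rate.

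Neither part can be sized from the document. The false differences above are illustrations on assumed inputs, not estimates for this trial. The importance is moderate: this is a secondary outcome of a feasibility study, but one whose data quality is a primary question and whose counts feed the next trial's design.

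**What to change.** 1. Add a prompted/unprompted code to both film categories, and count only unprompted requests in the outcome.
2. Instruct parents to tally only unprompted requests in the App, or add a separate button for prompted ones, so that App and film measure the same thing.
3. Keep viewing of the full films, but have the same coder re-score a small random subset of segments, with equal minutes per arm, at normal speed with sound. Report the detection rate separately for each code.

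Full viewing is preferable to scoring only a sample of every film. Scoring 25% of a film with 20 requests would leave about 5; under an assumed Poisson count the relative error rises from 1/√20 = 22% to 1/√5 = 45%, and the match with App totals over the same window is lost.

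The cost is modest extra coding time and one more judgement per episode. Films that have been kept can be re-scored. App tallies already taken without the distinction cannot be recovered, so the report should say which instruction parents had.
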